5.1 Inclusion/exclusion criteria

Inclusion Criteria

Patients eligible for inclusion in this study have to fulfill all of the following criteria:

1. Written informed consent must be obtained before any assessment is performed.
2. Male or female subjects aged 18-65 years.
3. Subjects with relapsing remitting MS defined by 2010 revised McDonald criteria (see [Appendix 4](#)).
4. Patients with Expanded Disability Status Scale (EDSS) score of 0-6.0 inclusive (see [Appendix 6](#)).
5. Patients stable on immunomodulatory treatment with fingolimod for at least 28 days and at most 4 months prior to screening according to local label
6. Neurologically stable with no evidence of relapse within 30 days prior to inclusion date (visit 2)
7. Sufficient ability to read, write, communicate and understand

Exclusion Criteria

Patients fulfilling any of the following criteria are not eligible for inclusion in this study:

1. Patients who have been treated with:

- systemic corticosteroids or immunoglobulins within 1 month prior to screening;
 - immunosuppressive medications such as azathioprine, cyclophosphamide, or methotrexate within 3 months prior to screening;
 - monoclonal antibodies (including natalizumab) within 3 months prior to screening;
 - mitoxantrone within 6 months prior to screening
 - cladribine at any time.
2. Patients with any medically unstable condition, as assessed by the primary treating physician at each site.
 3. Patients with any of the following cardiovascular conditions :
 - history of myocardial infarction or with current unstable ischemic heart disease;
 - Heart failure (NYHA III-IV) or any severe cardiac disease as determined by the Investigator (see [Appendix 5](#));
 - history or presence of a second-degree AV block, Type II or a third-degree AV block
 - patients receiving Class Ia (ajmaline, disopyramide, procainamide, quinidine) or III antiarrhythmic drugs (e.g., amiodarone, bretylium, sotalol, ibutilide, azimilide, dofetilide);
 - proven history of sick sinus syndrome;
 - uncontrolled hypertension
 4. Patients with severe respiratory disease, pulmonary fibrosis, or chronic obstructive pulmonary disease (Class III-IV).
 5. Patients with history of specific MRI findings (tumor, subdural haematoma, post-contusional changes, territorial stroke, neurodegenerative disorders, aneurysm/arteriovenous malformation, evidence of past macroscopic haemorrhage, or other relevant MRI findings that would interfere with evaluation)
 6. Any severe disability or clinical impairment that can prevent the patient to meet all study requirements at the investigator's discretion
 7. History of malignancy of any organ system, treated or untreated, within the past 5 years whether or not there is evidence of local recurrence or metastases, with the exception of localized basal cell carcinoma of the skin
 8. Patients who have received an investigational drug (excluding fingolimod) or therapy within 90 days or 5 half-lives of screening, whichever is longer.
 9. Pregnant or nursing (lactating) women, where pregnancy is defined as the state of a female after conception and until the termination of gestation, confirmed by a positive hCG test (serum)
 10. Patients with any ophthalmologic reason for RNFL pathology other than MS, such as: optic neuropathy, active advanced glaucoma, injury of the optic nerve based on the ophthalmologist's clinical judgment
 11. history or presence of severe myopia

- a. in patients who have not had refractive surgery, a refractive error of greater than 6.00 diopters
 - b. pathologic fundus changes of high myopia, such as retinal pigmentary atrophy, besides peripapillary atrophy (atrophy involving the macula) or a staphyloma
 - c. in patients that have had previous refractive surgery, an axial eye length of greater than 26 mm
12. Acute optic neuritis within the past 6 months before screening
 13. Evidence of advanced, non-proliferative or proliferative diabetic retinopathy
 14. Presence of retinal conditions associated with edema, subretinal fluid, cysts, etc.
 15. Concomitant use of drugs that may directly affect retinal structure and function (e.g. chronic systemic corticosteroids [>30 consecutive days; doses higher than Cushing threshold e.g. prednisone 7.5mg/d], intraocular anti-angiogenic drugs [ranibizumab, bevacizumab], intraocular steroids etc.)

5.2 Premature patient withdrawal

Patients must be withdrawn from the study for any of the following reasons:

- Withdrawal of informed consent
- Investigator's decision (withdrawn in the best interest of the patient for any reason)
- Use of prohibited medication (see section 6.4 Prohibited Treatment)

Patients should be withdrawn at any time if the investigator concludes that it would be in the patient's best interest for any reason. Protocol violations should not lead to patient withdrawal unless they indicate a significant risk to the patient's safety.

Patients may voluntarily withdraw from the study for any reason at any time. They may be considered withdrawn if they state an intention to withdraw, or fail to return for visits, or become lost to follow up for any other reason.

If premature withdrawal occurs for any reason, the investigator must determine the primary reason for a patient's premature withdrawal from the study and record this information on the Study Completion CRF.

For patients who are lost to follow-up (i.e., those patients whose status is unclear because they fail to appear for study visits without stating an intention to withdraw), the investigator should show "due diligence" by documenting in the source documents steps taken to contact the patient, e.g., dates of telephone calls, registered letters, etc.

Patients who are prematurely withdrawn from the study will not be replaced by newly enrolled patients.

6 Treatment

6.1 Patient numbering

Each patient is uniquely identified in the study by a combination of his/her center number and patient number. The center number is assigned by Novartis to the investigative site. Upon

signing the informed consent form, the patient is assigned a patient number by the investigator. At each site, the first patient is assigned patient number 1, and subsequent patients are assigned consecutive numbers (e.g. the second patient is assigned patient number 2, the third patient is assigned patient number 3). Once assigned to a patient, a patient number will not be reused. If the patient fails to be enrolled for any reason, the reason for not being enrolled will be entered in the CRF and demography should also be completed.

6.2 Investigational treatment

MS medication: Fingolimod (FTY720) 0.5 mg per capsule (hard gelatin capsules) is used to be taken p.o. once daily. Fingolimod will be prescribed according to local label. The decision to prescribe Fingolimod will be made independent of this study.

6.3 Concomitant treatment

All concomitant medications taken within 30 days prior to Screening (Visit 1) and during the study must be recorded on the appropriate CRFs. The investigator should instruct the MS patients to notify the study site about any new medications he/she takes after the start of the study.

6.4 Prohibited treatment

Patients who have met exclusion criteria for exclusionary medications will not be allowed to join the study. Concomitant use of drugs that may directly affect retinal structure and function (e.g. chronic [>30 consecutive days; doses higher than Cushing threshold e.g. prednisone 7.5 mg/day] systemic corticosteroids, intraocular anti-angiogenic drugs [ranibizumab, bevacizumab] etc.) is not allowed during the study and these participants will have to be withdrawn from the study.

Once the patient has entered the study at Visit 1 and while the patient is on fingolimod therapy, use of the following treatments are NOT allowed concomitantly:

- Immunosuppressive medication (e.g. cyclosporine, azathioprine, methotrexate, cyclophosphamide, mitoxantrone, cladribine);
- Other concomitant medications: immunoglobulins, monoclonal antibodies (including natalizumab), IFN- β , glatiramer acetate, adrenocorticotrophic hormone (ACTH)

The administration of any live or live attenuated vaccines (including for measles) is prohibited while patients are receiving fingolimod and for 12 weeks after fingolimod discontinuation. They may be administered thereafter, once there is confirmation that lymphocyte counts are in the laboratory normal range.

6.5 Discontinuation of study treatment and premature patient withdrawal

Study drug must be discontinued for a given patient if the investigator determines that continuing it would result in a significant safety risk for that patient. The following circumstances require study drug discontinuation:

- Intolerability of study medication (fingolimod)

- The occurrence of an adverse event or clinically significant abnormality that, in the judgment of the investigator, warrants discontinuation of treatment
- Use of prohibited medications, listed in section 6.4

In addition, the following conditions based on safety monitoring guidelines (See [Appendix 7](#)) should result in fingolimod interruption or discontinuation:

- Ophthalmic:
 - Diagnosis of macular edema
 - Decrease in visual acuity or cystic changes in the macula
- Hepatic:
 - Repeated confirmation of an increase in ALT > 5 x ULN
 - Repeated confirmation of an increase in AST > 5 x ULN
- Blood lymphocyte count less than 100/mm³
- New neurological symptoms accompanied by MRI findings (according to local practice) unexpected for MS

In case of a decrease of visual acuity an immediate ophthalmologic assessment is required. After exclusion of a macula edema or cystic changes in the macula treatment can be continued.

Permanent study drug discontinuation **is required** upon diagnosis of cancerous skin disorders or pregnancy.

Furthermore, all criteria listed under 5.2 for premature patient withdrawal will automatically lead to study drug discontinuation.

In addition to these requirements for study drug discontinuation, the investigator should discontinue study drug for a given patient if, on balance, he thinks that continuation would be detrimental to the patient's well-being.

In addition to scheduled visits, patients who discontinue study drug due to adverse events or abnormalities on safety monitoring tests must be followed up with additional visits as needed in order to confirm the resolution of abnormalities.

Document the date and primary reason for stopping the study drug on the appropriate page of the CRF.

For re-initiation after treatment interruption the same first dose monitoring as for treatment initiation should be repeated if treatment is interrupted for:

- One day or more during the first 2 weeks of treatment
- More than 7 days during weeks 3 and 4 of treatment
- More than 2 weeks after 4 weeks of treatment

If the treatment interruption is of shorter duration than the above, the treatment should be continued with the next dose as planned. It is recommended not to initiate or change dosages of digoxin, beta-blockers and calcium-channel blockers treatment due to a possible additive effect on heart rate reduction. In case these are already initiated advice from a cardiologist is necessary according to local label. If study medication is restarted as per protocol, a reason for the interruption of treatment and time of interruption should be appropriately documented in the source documents as well as in the CRF.

The following examinations regarding cardiac response observation have to be performed at re-start of study drug:

- 12-lead ECG prior to and after 6 hours of first administration
- Continuous 6-hour ECG is recommended
- measurement of blood pressure and heart rate (every hour)

In case of clinically significant abnormalities during or at the end of the 6 hours observation (criteria defined in the local label), cardiac monitoring will be prolonged and surveillance measures implemented as recommended in the label (see also Appendix 7). If study medication is restarted, the reason for the interruption of treatment and time of interruption should be appropriately documented in the source documents as well as in the CRF.

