In case of detection of elevated ALT/AST values > 5 times the upper limit of the normal range (ULN), additional blood chemistry panel including ALT, AST, AP, GGT, total and conjugated bilirubin, albumin should be performed.

If ALT/AST values are repeatedly 5 times the ULN, the study drug must be suspended and not resumed until values have normalized. Patients who develop symptoms suggestive of hepatic dysfunction such as unexplained vomiting or jaundice, should have liver enzymes checked and fingolimod should be discontinued if significant liver injury is confirmed.

In case of isolated elevation of bilirubin over 2.0 mg/dl (34.2 $\mu\text{mol}/\text{L}$), the investigator must discontinue fingolimod administration. Additional evaluations may be performed at the discretion of the investigator.

An interruption or discontinuation of the study drug should be clearly documented and reflected on Dosage Administration Record CRF. AE/SAEs need to be filed as appropriate.

Guidance on monitoring of patients with notable lymphopenia

Fingolimod results in sequestration of a proportion of the circulating lymphocytes in lymph nodes with resultant reduction in circulating lymphocyte counts. Average circulating lymphocytes counts are expected to be around $0.5 - 0.6 \times 10^9 / \text{L}$ or 500- 600 cells/ mm^3 . As such, the absolute total WBC, neutrophil and lymphocyte counts will be measured at each visit by the local laboratory. In case of lymphocyte alert, lymphocyte count should be

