repeated in two weeks by the local laboratory. If the repeat test confirms the lymphocyte count is below $0.1 \times 10^9/L$ or 100 cells/mm^3 , the study drug must be discontinued and the lymphocytes count needs to be monitored every two weeks until levels reach $0.6 \times 10^9/L$ values. Recovery of lymphocyte counts is expected to take several weeks given the long half-life of fingolimod. The patient should be evaluated and monitored for infections on a regular basis during this period. As shown recently (data presented at AAN 2011: S30.001 Lymphocytes and Fingolimod-Temporal patterns and relationship with infections) a lymphocyte count between $100\text{-}200 \text{ cells/mm}^3$ is not associated with a higher infection risk. Therefore, a cut-off of 100 cells/mm^3 is regarded as appropriate for this study. After termination of the study the recommendations defined in the local label will prevail, in Germany a limit of 200 cells/mm^3 will be considered in agreement with the SmPC.

Re-initiation of the study drug can only be considered once the lymphocyte counts increase above 600 cells/mm^3 as confirmed by the local lab after discussion with the Clinical Trial Leader at Novartis.

Guidance on monitoring of patients with symptoms of neurological deterioration, inconsistent with MS course

Should a patient develop any manifestations that, in opinion of the investigator, are atypical for multiple sclerosis including unexpected neurological or psychiatric symptom/signs (e.g. rapid cognitive decline, behavioral changes, cortical visual disturbances or any other neurological cortical symptoms/sign), or any symptom/sign suggestive of an increase of intracranial pressure or accelerated neurological deterioration, the investigator should schedule a complete physical and neurological examination and an MRI as soon as possible and before beginning any steroid treatment. Conventional MRI as defined in the protocol as well as Fluid-attenuated Inversion Recovery (FLAIR) and Diffusion-weighted imaging (DWI) sequences are recommended for differential diagnosis of Posterior reversible encephalopathy syndrome. The MRI must be evaluated by the local neuroradiologist. The investigator will contact the Clinical Trial Leader at Novartis to discuss findings and diagnostic possibilities as soon as possible. AE/SAEs need to be filed as appropriate.

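### Protocol 6.5 and Appendix 7 do not state the same safety triggers for stopping fingolimod: three of four condition groups differ, and one eye case is in direct conflict

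*Protocol*

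**What the plan says.** Protocol 6.5 introduces a list of conditions by reference to the guidance in Appendix 7 and says that they "should result in fingolimod interruption or discontinuation". The list has four groups.

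- **Ophthalmic.** 6.5 lists diagnosed macular edema, and separately "Decrease in visual acuity or cystic changes in the macula". A later sentence asks for immediate ophthalmologic assessment of an acuity decrease and lets treatment go on once edema or cysts are ruled out. Appendix 7 makes discontinuation mandatory on either of two criteria: diagnosed edema, or an acuity loss of two lines or more together with an abnormal OCT. Abnormal means central foveal thickness more than 20% above baseline, or foveal cysts.
- **Lymphocytes.** 6.5 lists "Blood lymphocyte count less than 100" per mm³ and stops there. Appendix 7 says "In case of lymphocyte alert, lymphocyte count should be" "repeated in two weeks by the local laboratory". It goes on: "If the repeat test confirms the lymphocyte count is below" 100 cells/mm³, "the study drug must be discontinued and the lymphocytes count needs to be monitored every two weeks".
- **Hepatic.** 6.5 has two bullets, the first being "Repeated confirmation of an increase in ALT" above 5 x ULN and the second the same for AST. Appendix 7 suspends drug on repeated ALT/AST elevation at that level. It also requires discontinuation for an isolated bilirubin above 2.0 mg/dl.
- **Neurological with MRI.** Both texts act on MRI findings that MS would not explain.

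**The concern.** A section that names another as its source should give the same rule. Here a site reading only 6.5 and a site reading only Appendix 7 can handle the same result differently. The omission of a repeat lymphocyte count stands out because the ALT and AST bullets in the same list do ask for confirmation.

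What is at stake is consistent handling of safety findings. Sites will hold the data on which the texts diverge: Protocol 7.2 and Appendix 7 make acuity and OCT part of the ophthalmologic examination, with central foveal thickness measured, and blood counts are routine. The SAP reports treatment interruptions (2.4.1) and separates adverse events leading to temporary interruption from those leading to permanent discontinuation (2.8.1). Uneven handling could therefore move a patient between reported categories. The documents do not allow that to be sized.

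**Working it through.** No figure in the plan depends on this point, so the check compares the texts.

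**Eye.** Let A be an acuity loss of two lines or more, C cystic changes, and T thickening above 20%. Assume that macular edema has been looked for and excluded, since diagnosed edema is listed in both texts. Read the 6.5 continuation sentence as requiring both edema and cysts to be excluded. Then:

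- 6.5 lists the patient if A or C, and permits continuation if A without C.
- Appendix 7 requires discontinuation if A and (T or C).

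| Findings | 6.5 | Appendix 7 | Comparison |
|---|---|---|---|
| none | not listed | not listed | agree |
| T | not listed | not listed | agree |
| C | listed | not listed | scope differs |
| C, T | listed | not listed | scope differs |
| A | listed, may continue | not listed | agree in effect |
| A, T | listed, may continue | discontinuation mandatory | direct conflict |
| A, C | listed | discontinuation mandatory | both act |
| A, C, T | listed | discontinuation mandatory | both act |

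Of 8 combinations, 5 raise no difference in whether the texts act, 2 differ in scope, and 1 conflicts (5 + 2 + 1 = 8). These are logical cases, not probabilities. A loss of less than two lines with cysts is a further difference in scope, because 6.5 sets no size for the loss. In the A, T row the patient does enter the 6.5 list through the acuity decrease; it is the continuation sentence that releases the patient.

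**Lymphocytes.** The cut-off is 100/mm³ in both texts. Appendix 7 does not define its alert; it is read here as the notable value below 100/mm³ in Appendix 3.

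| Result | 6.5 | Appendix 7 |
|---|---|---|
| first count < 100/mm³ | interrupt or discontinue | repeat in two weeks; nothing on drug meanwhile |
| repeat count < 100/mm³ | interrupt or discontinue | discontinuation mandatory |

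Length of the unaddressed interval: if each result takes t days and the repeat is drawn on day 14, the first result is known on day t and the second on day 14 + t. The gap is (14 + t) - t = 14 days. At one capsule daily (Protocol 6.2) that is 14 x 1 = 14 doses, taken or withheld. A 14-day hold just reaches, without exceeding, the limit of more than two weeks beyond which 6.5 asks for first-dose monitoring to be repeated in patients past week 4.

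**Hepatic.** The ALT/AST triggers agree in substance (repeated, above 5 x ULN). Bilirubin: mandatory discontinuation in Appendix 7, no entry in the 6.5 hepatic bullets.

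**Neurological with MRI.** Agree in substance.

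**Count.** Groups that differ: ophthalmic, lymphocyte, hepatic = 3 of 4.

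**The case against.** The strongest reply is that most of this is compatible. A broad list of reasons to interrupt or stop, and a narrower list of reasons why drug has to stop, can both be obeyed. Interrupting on a first low count and discontinuing on confirmation meets both lymphocyte texts. Acting on cysts without acuity loss meets 6.5 and breaches nothing in Appendix 7. An isolated raised bilirubin can be handled under the general clause in 6.5 on clinically significant abnormalities. All of that stands, so these are differences of scope. What remains is that neither text tells the site to combine them in this way.

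On the eye case, the reply is that thickening is itself grounds for suspecting edema under the baseline rule in Appendix 7, so edema has not been excluded and the 6.5 continuation sentence is not met. Appendix 7 also places its stopping criteria under possible macular edema and follows these patients on a schedule dated from its diagnosis. This narrows the point: thickening on OCT alone does not release the patient under 6.5. It does not remove it. Appendix 7 lists the acuity-plus-OCT criterion apart from diagnosed edema, and treats thickening at baseline as a suspicion that angiography may help to resolve. Once edema and cysts are excluded, one text permits what the other forbids.

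Investigators may also stop drug at any time on safety grounds, and Appendix 7 expects average counts of 500 to 600/mm³, well above the cut-off. Both are fair and limit the likely reach. Neither gives sites a common rule.

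**Conclusion.** The point holds, and should be fixed, with one direct conflict and several differences of scope. The conflict is an acuity loss of two lines or more with thickening above 20%, no cysts, and edema actually excluded. The differences of scope are cysts without a two-line loss, the single versus repeated lymphocyte count, and isolated bilirubin. Three of the four condition groups are affected; ALT/AST and neurological/MRI agree in substance.

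It rests on two readings: that the undefined lymphocyte alert means a count below 100/mm³, and that the 6.5 continuation sentence requires both edema and cysts to be excluded.

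A reader might infer more than the documents support:

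- That every difference is a contradiction. Only the thickening case is.
- That the thickening case is missed by 6.5 altogether. It is listed there, then may be released.
- That foveal thickening by itself puts the texts in conflict. It does not while edema remains unexcluded.
- That the RNFLT results are affected. Nothing in the documents shows this, and no such effect is claimed.

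The documents give no frequency of affected patients, so the number at risk of different handling is unknown.

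**What to change.** Reconcile Protocol 6.5 with the liver, lymphopenia and macular edema guidance in Appendix 7, so that both sections state the same trigger and the same action (interruption or discontinuation) for each condition. The wording should settle:

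- which text governs an acuity loss of two lines or more with thickening above 20%, once edema and cysts are excluded;
- how cystic changes without a two-line loss are classed when edema is not diagnosed;
- what a lymphocyte alert is, and what applies between a first low count and its repeat;
- whether the bilirubin condition belongs in the 6.5 list.

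Which rule applies in each case is for the sponsor's clinical and safety functions to decide; this review takes no view.

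The cost is a wording amendment, with the approvals that Appendix 1 requires, and a communication to sites. No new procedure or data collection is needed. Amendment 2 already adjusted the liver wording in 6.5 and Appendix 7 together, so there is a precedent. The change helps only while patients are still being treated on study, which the documents do not establish.

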10.3 Treatments (study drug, rescue medication, other concomitant therapies, compliance)

All patients will receive a dose of 0.5 mg fingolimod daily according to local label. No study drug will be provided.

Concomitant therapy used both prior to and after start of study drug administration will be summarized by treatment group. The WHO Drug Reference Guide will be used for coding of medications.

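### Protocol 6.5 makes every 5.2 withdrawal, including withdrawal of consent, end fingolimod automatically, although 6.2 makes prescribing independent of the study

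*Protocol*

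**What the plan says.** Protocol 6.5, after its list of safety reasons for stopping or interrupting treatment, adds: "Furthermore, all criteria listed under 5.2 for premature patient withdrawal will automatically lead to study drug discontinuation". The bulleted list in 5.2 has three entries: "Withdrawal of informed consent"; the investigator's decision, explained as "withdrawn in the best interest of the patient for any reason"; and use of prohibited medication. Section 5.2 then adds in running text: "Patients may voluntarily withdraw from the study for any reason at any time". It also allows patients who miss visits or are lost to follow-up to be considered withdrawn.

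On the drug itself, 6.2 says "Fingolimod will be prescribed according to local label" and "The decision to prescribe Fingolimod will be made independent of this study". Section 10.3, repeated in section 11, says "No study drug will be provided". Inclusion criterion 5 in 5.1 requires "Patients stable on immunomodulatory treatment with fingolimod for at least 28 days and at most 4 months prior to screening according to local label".

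**The concern.** The study observes patients who already take fingolimod on prescription. Leaving such a study should end data collection, and treatment should remain a matter for the patient and the treating physician. The 6.5 sentence says instead that leaving ends the drug, with no exception for exits that have nothing to do with safety.

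Voluntariness and patient safety are at stake. A patient who uses the right to withdraw would, if a site applied the sentence as written, lose an MS drug for no medical reason. A later restart also has a cost. Section 6.5 asks for repeat first-dose monitoring when treatment has been interrupted for more than 2 weeks after 4 weeks of treatment. Appendix 7 describes that monitoring as at least 6 hours of observation with ECGs and hourly blood pressure and heart rate, because recommencing can lower heart rate and delay AV conduction.

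**Working it through.** The point is textual. There is no planned figure to reproduce and no formula to apply.

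**Step 1. What does study drug mean in 6.5?** The section's first bullet names fingolimod in brackets as the study medication. The same section uses the term for actual intake: permanent discontinuation for pregnancy or cancerous skin disorders, and cardiac monitoring when the drug is restarted. The natural reading of the quoted sentence is that the patient stops taking fingolimod.

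**Step 2. What does the sentence add to the other rules in 6.5?** Those rules cover safety risk, intolerability, adverse events, prohibited medication, named ophthalmic, hepatic, lymphocyte and neurological findings, skin cancer, pregnancy, and detriment to well-being.

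| 5.2 criterion | Stopped by another 6.5 rule? | Added by the quoted sentence |
|---|---|---|
| Withdrawal of consent | No | The whole drug stop |
| Investigator's decision, any reason | Yes, where it rests on safety or well-being | A stop for best-interest exits unrelated to the drug |
| Prohibited medication | Yes, listed by name | Nothing |

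Whether voluntary exit, missed visits and loss to follow-up count as listed criteria is not clear, since they stand in the running text of 5.2 and not in its bullets. Where they do count, no other 6.5 rule stops the drug for them either.

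**Step 3. Which sections does this meet?**
- *6.2* is the section in arguable conflict. A prescription decided independently of the study should not end because participation ends.
- *10.3 and 11* say who supplies the drug, and *5.1* says when it was started. Neither says when it must stop. They are context: the study neither started nor supplies the drug, so a consent withdrawal gives it no evident ground for stopping it.

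**Step 4. Does any text limit the sentence?** None was found. The nearest is in the lymphopenia guidance of Appendix 7, where the local label governs once the study has ended. That concerns the lymphocyte limit after study termination and not a patient who leaves early. Elsewhere the protocol keeps the two events apart. The glossary defines premature withdrawal as leaving the study and does not mention the drug. Appendix 7 stops the drug for macular edema while encouraging the patient to remain in the study.

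**Step 5. How many patients?** The documents give no consent-withdrawal rate. With approximately 100 planned, 1% is 0.01 × 100 = 1 patient. Inclusion criterion 5 means that everyone has had at least 28 days (28 / 7 = 4 weeks) of fingolimod before screening. The restart threshold that applies is therefore the one of more than 2 weeks.

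**The case against.** The best answer is that the sentence is standard wording from trials that supply their drug, and that here it means only the end of recorded study treatment. There is support for this. The lymphopenia guidance presupposes that fingolimod may continue under the label after the study. SAP 2.4.1 takes the last administration from the study completion form, the form on which Protocol 5.2 has the withdrawal reason recorded. The protocol also names no means of stopping a former participant's prescription. In addition, 6.2 can be read as covering only the decision to start, and the protocol imposes other stopping rules without contradicting it.

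Part of this stands. The sentence is more plausibly a drafting slip than an intention to remove treatment. But the softer meaning is stated nowhere, and the same section uses the same term for real cessation. The other stopping rules rest on safety or on prohibited drugs; this one extends to exits with no medical reason.

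Three stronger readings are tempting, and the documents do not support them:
- *That 6.5 contradicts 10.3, 11 and 5.1 outright.* It does not; they concern supply and start of the drug.
- *That patients are told they will lose their drug if they leave.* Appendix 1 places the consent form in a separate document, which was not available. It may say the opposite, in which case it and 6.5 would disagree.
- *That the results are affected.* No endpoint, analysis set or safety table depends on the sentence.

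**Conclusion.** The sentence is wrong as written, and the point is minor. It is inconsistent with 6.2 and is the only rule in 6.5 by which withdrawal of consent ends fingolimod. Confidence in the reading of the text is high.

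Confidence in the harm is moderate. It assumes that sites apply the sentence literally and that the consent form does not tell patients otherwise. The number of patients affected cannot be estimated from the documents. It is limited to those among the approximately 100 planned who leave for a non-medical reason while still on fingolimod.

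**What to change.** Replace the quoted sentence in 6.5 with:

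> Study withdrawal under 5.2 leads to discontinuation of fingolimod only where the reason is use of prohibited medication or an investigator decision based on drug safety or the patient's medical well-being. Withdrawal of consent, loss to follow-up or other non-medical study exit does not in itself require discontinuation; continuation is decided by the treating physician and the patient under the local label.

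Simple deletion would be less good. It would leave medically based investigator withdrawals to the remaining rules, some of them discretionary, whereas this wording keeps an explicit stop for them. All other rules in 6.5 stay as they are. The consent form should be checked for agreement with the new text.

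The cost is one amended passage in the protocol. The SAP, the CRF and the analyses do not change.
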